4.4 Sensitivity analyses

Sensitivity analyses will be carried out for the primary efficacy endpoint (change in HbA1c from baseline (week 0) to week 52) only. These sensitivity analyses will be as follows

- Mixed Model Repeated Measures (MMRM) using the Per-Protocol analysis set,
- ANCOVA using values prior to rescue treatment (LOCF will be used if the week 52 value is not available)
- The MMRM model will be repeated including all values according to the ITT principle (i.e. all values will be included regardless of use of rescue treatment or treatment discontinuation)

Further details of these sensitivity analyses is provided in Section 4.8.4.

4.5 Definitions

4.5.1 Baseline values

For all efficacy variables, the baseline value will be the last non-missing value on or prior to the first dose of the double-blind study drug date or the last non-missing value of the visit 1 or visit 2 assessment for those subjects without a first dose start date.

The baseline value of each safety laboratory test or physical exam endpoint is defined as the last assessment (either numerical or character value) on or prior to the first dose of double-blind study drug date or the last non-missing value of the visit 1 or visit 2 assessment for those subjects without a first dose start date.

4.5.2 Derived data

The waist:hip ratio is calculated as: waist circumference (cm) / hip circumference (cm).

To convert HbA1c from mmol/mol to % the following conversion factor will be used:

$$HbA1c$$
 (%) = (0.09148* $HbA1c$ (mmol/mol)) + 2.152

4.5.3 Change from baseline

Change from baseline to any week t in the double-blind treatment period is defined as follows:

$$C_{week\ t} = M_{week\ t} - M_{baseline}$$

where a) $C_{week t}$ is the change from baseline at week t, b) $M_{week t}$ is the measurement at week t, and c) $M_{baseline}$ is the measurement at baseline.

4.5.4 Longitudinal repeated measures analysis

A longitudinal repeated measures analysis using restricted maximum likelihood (REML) will be performed for the primary efficacy endpoint and three of the secondary endpoints (change in weight from baseline to week 52, change in FPG from baseline to week 52 and change in SBP from baseline to week 52). The SAS procedure PROC MIXED will be used. The preferred model will include the fixed categorical effects of treatment, week and treatment-by-week interaction as well as the continuous fixed covariates of baseline measurement and baseline measurement-by-week interaction.

This method involves implementing a linear mixed effects model of the form:

$$C_{ijk} = intercept + \beta_1 [M_{baseline,ij}] + \tau_i + \alpha_k + (\alpha \tau)_{ik} + (\alpha M_{baseline})_{ijk} + error_{ijk}$$

where

- C_{ijk} is the change from baseline for patient j in treatment group i at time k.
- β_1 is the slope coefficient for the baseline measurement
- $M_{baseline,ij}$ is the baseline measurement for patient j in treatment group i
- τ_i is the mean effect for treatment group i
- α_k is the mean effect at time k
- $(\alpha \tau)_{ik}$ is the interaction term between treatment group i and time k
- $(\alpha M_{baseline})_{ijk}$ is baseline measurement-by-week interaction term for patient j in treatment group i at time k
- $error_{ijk}$ is the error term for patient j in treatment group i at time k

The above model incorporates repeated measures (where measurements are taken repeatedly on the same patient i.e., at baseline, week 2, week 4 up to week 52). Hence, the primary model is a mixed model repeated measures (MMRM). The model will be used to derive a least-squares estimate of the mean treatment difference with corresponding 2-sided 95% CI.

An unstructured matrix for the within-subject error variance-covariance will be used. The Kenward-Roger approximation will be used to estimate denominator degrees of freedom (DDFM).

In case of non-convergence of the preferred model or memory space issues, the following back-up models will be defined:

- The first backup model is the same as the preferred model but the Kenward-Roger method will be replaced by Satterthwaite approximation
- The second backup model is the same as the preferred model but without the term for baseline measurement-by-week interaction

The second back-up model will only be provided if the first back-up model does not converge or has memory issues.

4.5.4.1 Adjustment for baseline imbalances

Clinically important imbalances between treatment groups with respect to baseline characteristics will be identified using summaries of baseline data by treatment group. Any imbalances will be assessed from a clinical perspective (without performing statistical testing). If clinically important imbalances are found (e.g., between countries), they may be adjusted for in the analysis by including the corresponding baseline characteristics as additional covariates in the model, e.g., a fixed effect for country may be added to the MMRM model.

4.5.4.2 Assessment of Treatment-by-Baseline interaction

Treatment-by-baseline interaction will be assessed for the analyses of the primary efficacy endpoint. In the repeated measures model, the interaction will be tested by including the additional terms for the treatment-by-baseline interaction (treatment-by-baseline HbA1c and treatment-by-baseline HbA1c-by-week).

The treatment-by-baseline HbA1c-by-week interaction will be assessed using contrasts of the treatment effect by baseline HbA1c at Week 52. The test for interaction will be performed at the 0.10 level of significance. If the interaction is not significant, the original model will be used (see section 4.5.4). Otherwise, the interaction will be assessed as qualitative or quantitative. Assessment of the interaction type will be based on regression lines plotted for each treatment group. The intercepts and slopes for these regression plots will be obtained from the analysis model including the interaction term. The intercepts will be estimated by the

least squares treatment means. The horizontal axis of the plots will range from the minimum baseline value from all subjects included in the analysis to the maximum baseline value.

If the regression lines do not cross, or the crossing is judged not severe (i.e., the crossing occurs near the boundary or beyond the range of baseline values), then the interaction will be considered quantitative and this does not compromise the validity of the treatment comparisons. In this case, the treatment comparisons will be made using the original model without the interaction term.

Otherwise, the interaction will be considered qualitative and treatment comparisons will not be presented as a result of the original model. In this case, the impact of the baseline value on treatment effect will be investigated by summarizing the data in subsets defined by baseline categories.

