4.2.1 Objectives and hypotheses

The combination of metformin and a sulphonylurea (glimepiride) is a standard therapy in the treatment of type 2 diabetes and has been shown to reduce HbA1c.

The primary objective of this study is to demonstrate the non-inferiority of dapagliflozin and dapagliflozin plus saxagliptin as add-on therapies to metformin compared to glimepiride as add-on therapy to metformin for the primary efficacy variable (change in HbA1c from baseline to week 52).

The null hypothesis H_0 (given below) will be tested against the alternative hypothesis H_A ($\alpha = 0.025$, one-sided):

$$H_0$$
: $\mu_t - \mu_c \ge 0.30\%$,

$$H_A$$
: $\mu_t - \mu_c < 0.30\%$

where μ_t denotes the mean absolute change in HbA1c from baseline to week 52 in patients treated with dapagliflozin added to metformin and dapagliflozin plus saxagliptin added to metformin (test medication); μ_c denotes the mean absolute change in HbA1c from baseline to week 52 in patients treated with glimepiride added to metformin (active control). The non-inferiority margin is determined to be 0.30% (in absolute terms). A difference of 0.30% or

less, in HbA1c change from baseline to week 52 between the treatment groups, is considered clinically equivalent (from a medical point of view). Non-inferiority will be assessed using the 2-sided 95% Confidence Interval (CI) of the adjusted mean difference between dapagliflozin or dapagliflozin plus saxagliptin and glimepiride. If the upper limit of the 2-sided 95% CI is less than 0.30% then dapagliflozin or dapagliflozin plus saxagliptin will be considered to be non-inferior to glimepiride.

To preserve the Type I error \leq 0.025 (one-sided), a hierarchical testing procedure will be used as follows:

- First test dapagliflozin plus saxagliptin versus glimepiride
- If non-inferiority is achieved then test dapagliflozin versus glimepiride

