4.8.1 Primary Efficacy Analysis

The primary efficacy variable is the change in HbA1c from baseline to week 52 in the double-blind treatment period. The primary efficacy analysis will be based on the Full Analysis Set including values prior to rescue treatment or discontinuation. Values recorded after rescue treatment for those patients who used rescue medication or values collected more than 8 days after last dose date for patients who stayed more than 8 consecutive days off treatment are excluded from the analysis.

The primary efficacy variable will be analysed using the MMRM model (Section 4.5.4) with fixed effects for treatment group and covariates (baseline HbA1c; week (week 2 to week 52), and interactions baseline HbA1c-by-week and treatment group-by-week). Point estimates and 95% CIs will be calculated for the adjusted mean changes from baseline within each treatment group as well as for each comparison versus control in adjusted mean changes. The Kenward-Roger approximation will be used to estimate denominator degrees of freedom (DDFM) while an unstructured variance will be used to model the within-patient errors.

The primary assessments of efficacy will be a comparison of each of the 2 test groups: the dapagliflozin plus saxagliptin added to metformin versus the control group (glimepiride added to metformin) - and the dapagliflozin added to metformin versus the control group - using a 2-sided 95% CI. In particular, if the observed upper limit from a 2-sided 95% CI for the

difference in adjusted means is less than 0.30%, then the test group will be considered to be non-inferior to the control group.

Multiplicity will be controlled using a sequential testing scheme: the dapagliflozin plus saxagliptin added to metformin group will be tested versus the glimepiride group first, followed by the dapagliflozin plus metformin group versus the glimepiride group. If the first comparison is non-inferior the second comparison will be tested. Otherwise, significance testing will stop at the first comparison and the second comparison will be reported descriptively. See Section 4.2.1 for details. A superiority test of the dapagliflozin plus saxagliptin added to metformin group versus the glimepiride added to metformin group will also be conducted using the same modelling approach as for the primary non-inferiority analysis.

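### The primary non-inferiority comparison can be withheld after a 0.10-level interaction test and a visual judgement with no cut-off, and no replacement confirmatory test is named

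*SAP*

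**What the plan says.** The decision rule appears in section 4.2.1 ("If the upper limit of the 2-sided 95% CI is less than 0.30% then dapagliflozin or dapagliflozin plus saxagliptin" is declared non-inferior) and again in section 4.8.1, where, if the upper limit for the "difference in adjusted means is less than 0.30%, then the test group will be considered to be" non-inferior. Section 4.8.2 repeats it and then opens the key secondary tests. None of the three refers to an interaction test. On the model, section 4.8.1 says: "The primary efficacy variable will be analysed using the MMRM model (Section 4.5.4) with fixed effects for treatment group".

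Section 4.5.4.2 is a subsection of that model section and applies to the primary endpoint. The three-way term "will be assessed using contrasts of the treatment effect by baseline HbA1c at Week 52. The test for interaction will be performed at the 0.10" significance threshold. If the result is significant, the interaction is classed as quantitative or qualitative: "Assessment of the interaction type will be based on regression lines plotted for each treatment group". It is quantitative if the lines do not cross, or if the crossing is judged not severe, explained as "the crossing occurs near the boundary or beyond the range of baseline values". In every other case, "Otherwise, the interaction will be considered qualitative and treatment comparisons will not be presented as a result of the original model". What is offered instead is that "the impact of the baseline value on treatment effect will be investigated by summarizing the data in subsets defined by baseline categories".

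Section 4.3.1 makes the key secondary tests conditional on a non-inferiority conclusion for the primary endpoint.

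**The concern.** The SAP holds two rules for its primary decision. One depends only on the confidence limit. The other can remove the comparison that supplies that limit. Nothing confirmatory replaces it: the category estimates in 4.5.4.3 carry no margin, non-inferiority test or multiplicity rule, and the analyses in 4.8.4 are sensitivity analyses.

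The trigger is also open in three respects:

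- No distance defines a crossing near the boundary.
- The text speaks of contrasts and then of a single test, so one joint test and one test per comparison are both possible.
- Three lines are plotted, and it is not said whether a crossing in one comparison withholds that comparison or both.

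The judgement is made on lines fitted by treatment group, that is, on comparative results. A chance interaction could therefore cost the trial its primary claim and all key secondary claims although the margin was met, and two analysts following the SAP could disagree on whether it does.

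**Working it through.** **Inputs from the SAP.** Section 1.3: margin 0.30%, SD 1.0%, one-sided 0.025, true difference 0, 290 evaluable per arm, about 95% power. Section 1.2.2: 1:1:1 allocation. Section 4.5.4.2: interaction level 0.10. Appendix II: Visit 1 HbA1c from 7.5% to 10.5%.

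**The stated design reproduces.** SE = 1.0 × √(2/290) = 0.0830. Power = Φ(0.30/0.0830 − 1.96) = Φ(1.65) = 95.1%. The n for 95% power is 2 × (1.96 + 1.645)² / 0.30² ≈ 289 per arm.

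**Why the rule bites at the planning value.** Two fitted lines cross at x = x̄ − (difference at x̄)/(difference in slopes), where x̄ is the mean baseline. With a true difference of 0 the numerator is small, so the crossing usually lies near the mean baseline. Most chance-significant interactions would then look qualitative.

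**Simulation.** Three arms of 290, residual SD 1.0, equal true slopes, and a week-52 ANCOVA standing in for the MMRM. The SAP gives no baseline distribution, so three shapes on 7.5–10.5% were assumed: truncated normal with mean 8.58 and SD 0.64, truncated normal with mean 8.35 and SD 0.57, and uniform. There were 20,000 trials per shape at zero difference and 10,000 per shape in each advantage scenario. A comparison counts as withheld if the interaction p is below 0.10 and the lines cross inside the observed baseline range after a boundary zone is cut from each side. A withheld comparison counts as no claim. Ungated power was 94.8–95.1% for the first comparison and 91.0–91.4% for both.

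Results at true difference 0, over the three shapes, with zones of 10–30% per side unless stated:

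| Reading of 4.5.4.2 | Withheld | First-comparison power |
|---|---|---|
| Joint test, either crossing withholds both | 6.6–9.9% | 85.5–88.6% |
| Joint test, own crossing only | 4.6–8.5% | 86.6–90.5% |
| Test per comparison, own crossing only | 4.9–10.0% | 85.4–90.2% |
| Test per comparison, either crossing withholds both | 8.9–17.4% | 78.4–86.4% |
| Joint, either; only the central 20% of the range counts | 2.6–6.4% | 88.7–92.5% |

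In the first row, power for both comparisons is 82.1–85.1%. First-comparison power of 85.5–88.6% is what the ungated test would have with about 202–223 per arm. As a check, a joint 0.10 test with no true interaction should withhold no more than about 10%, and it does not exceed that.

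**Independent repeat.** 3,000 trials per scenario; baseline normal with mean 8.3 and SD 0.6 or 0.9 before truncation; slope −0.5; joint test, either crossing. Withheld: 9.3–9.9% if any crossing inside the range counts, and 8.5–9.2% if the outer 25% at each end is exempt. Power for both comparisons fell from about 91% to about 83%.

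**If the test arms are truly better** (joint, either; 10–30% zones). With both arms better by 0.1, 0.2 or 0.3, the withheld share is 6.2–9.9%, 2.3–8.4% or 0.3–5.4%. At an advantage of 0.2, ungated power is Φ(0.50/0.0830 − 1.96), essentially 100%. Gated first-comparison power is therefore about 100 − 8.4 = 91.6% to 100 − 2.3 = 97.7%; at 0.3 it is 94.6–99.7%. If only the combination arm is better, by 0.2, 6.7–10.0% are withheld, or 1.4–5.8% for the first comparison when only its own crossing counts.

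**The case against.** The strongest reply is that 4.5.4.2 speaks only of what is presented. It does not say that non-inferiority fails or that testing stops, and 4.2.1 and 4.8.1 define non-inferiority by the confidence limit alone. It is true that the consequence is inferred. But the deciding limit comes from the very comparison that is not presented, so a claim resting on it cannot be reported consistently with 4.5.4.2. If the other reading was intended, the SAP needs to say so.

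Section 4.8.1 does cite 4.5.4, so the rule is pre-specified and can be found. Section 4.5.4.2 also fixes the test level, the week-52 contrast, the source of the lines and the axis range. That narrows the discretion without removing it.

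The zero-difference case is unfavourable, and the 78.4% figure needs the harshest pairing of readings. Both points stand, though zero is the SAP's own planning value. The simulated ranges are not bounds: under 4.5.1 baseline is the last value on or before first dose, so the plotted range may exceed 7.5–10.5%.

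Finally, withholding an average effect when lines truly cross is a defensible aim, and a numeric crossing rule with a stated consequence would also cure the ambiguity. It would still lose power to chance interactions and would need a named replacement test.

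**Conclusion.** The concern holds. Section 4.5.4.2 conflicts with the unconditional rule in 4.2.1, 4.8.1 and 4.8.2, leaves its trigger partly to judgement on treatment-group results, and supplies no confirmatory substitute.

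At the planning values, a joint test with either crossing withholding both costs about 6 to 10 points of first-comparison power against the stated 95%. Other readings of the text give more or less. The loss shrinks as the true advantage of both test arms grows. These figures assume that a withheld comparison means no claim, that there is no true interaction, that the assumed baseline shapes are reasonable, and that a week-52 ANCOVA approximates the MMRM.

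The rule can only remove a claim, so it does not inflate type I error. A replacement test improvised after the comparison was withheld would put that at risk. Because the primary decision and every key secondary claim depend on this point, it must be settled before unblinding.

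**What to change.** 1. In 4.5.4.2, state that the non-inferiority decision and every step of 4.3.1 rest on the section 4.5.4 MMRM whatever the interaction result. Delete the sentence that withholds the comparisons.
2. Keep the interaction test, the plot (baseline HbA1c centred at its overall mean) and the baseline-category estimates of 4.5.4.3, labelled as supportive.
3. State whether the interaction test is joint or per comparison.

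The cost is SAP wording only. The one downside is that under a real qualitative interaction the average effect remains the headline result. The interaction test, the plot and the planned baseline HbA1c subgroup table would still show that interaction to the reader.

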4.5.4.3 Subgroup Analyses and Assessment of Treatment-by-Subgroup interaction

Treatment effects will be assessed across the following sub-groups: baseline HbA1c (<8%, $\ge 8\%$ - <9%, $\ge 9\%$), age group (<65, ≥ 65 - <75, ≥ 75 yrs), gender, female age group (≤ 50 , >50 yrs), race, country, and baseline eGFR (<30, ≥ 30 - <45, ≥ 45 - <60, ≥ 60 - <90, ≥ 90 mL/min/1.73m²). The analyses will be based on the primary model (see section 4.5.4). The estimates within each baseline HbA1c subgroup will come from the model with terms for treatment, week, baseline HbA1c category, treatment-by-week, treatment-by-baseline HbA1c category, time-by-baseline HbA1c category and treatment-by-time-by-baseline HbA1c category. Adjusted mean change from baseline and its difference from the control group will be given for each subgroup at week 52. The model to assess the treatment-by-baseline HbA1c interaction will include baseline HbA1c as a continuous variable (as per section 4.5.4.2).

Treatment effects within the remaining subgroups will come from the model including the fixed categorical effects of treatment, week, subgroup, treatment-by-week, treatment-by-subgroup, time-by-subgroup and treatment-by-time-by-subgroup as well as the continuous fixed covariates of baseline HbA1c and baseline HbA1c-by-week interaction. Tests of the treatment by subgroup interaction will be assessed using contrasts of the treatment effect by subgroups at Week 52. The model to assess the treatment-by-age interaction, the treatment-by-female age interaction and the treatment-by-baseline eGFR interaction will include age/baseline eGFR as a continuous variable.

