4.8.5 Subgroup analyses

The primary efficacy analysis will be repeated to summarize HbA1c within subgroups based on: age group ($<65, \ge 65 - <75, \ge 75$ yrs), gender, female age group ($\le 50, >50$ yrs), race, country, baseline HbA1c ($<8\%, \ge 8\% - <9\%, \ge 9\%$), and baseline eGFR ($<30, \ge 30 - <45, \ge 45 - <60, \ge 60 - <90, \ge 90$ mL/min/1.73m²). The primary MMRM model will be repeated as described in Section 4.5.4.3. The nominal p-value for the subgroup-by-treatment interaction at week 52 will be presented.

If the value of the grouping variable cannot be determined, the patient will be excluded from the corresponding subgroup analysis. For each subgroup analysis, if, in any treatment group, the number of patients is less than 10 for a subgroup, this subgroup will not be included in the interaction model and descriptive summaries only will be displayed. If there are problems with the convergence of the MMRM model, descriptive summaries within subgroups will be provided.

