7.2 Appendix II – Inclusion and Exclusion Criteria

Table 13. Patient inclusion and exclusion criteria

Inclusion criteria

- 1. Provision of informed consent prior to any study-specific procedures
- Is able to read, understand, and sign the Informed Consent Forms (ICFs) and, if applicable, an Authorisation to Use and Disclose Protected Health Information form, communicate with the Investigator, understand and comply with protocol requirements (including the use of diary and glucose meter measurements)
- 3. Is male or female of \geq 18 and \leq 75 years old at time of informed consent
- 4. Has a documented diagnosis of T2DM
- 5. Has a HbA1c of ≥7.5% and ≤10.5% based on central laboratory results from Visit 1, with individual need for therapy escalation
- 6. Currently treated with a stable MTD (≥1500 mg/day) of metformin therapy for at least 8 weeks prior to Enrolment visit
- 7. Has a BMI of \leq 45 kg/m² at enrolment visit
- 8. Has a C-peptide laboratory value of ≥1.0 ng/mL (0.33 nmol/L; 333.3 pmol/L) based on central laboratory results from Visit 1
- 9. For females only: women not of childbearing potential, or if they are women of childbearing potential (WOCBP), they must comply with the following:
 - Are not pregnant or breastfeeding
 - Have a negative urine pregnancy test result (minimum sensitivity 25 IU/L or equivalent units of human chorionic gonadotropin, beta subunit [βhCG]) at Visit 1 (Enrolment) and prior to randomisation.
 - Using or willing to adopt a highly effective method of birth control to avoid pregnancy throughout the study and for at least 4 weeks after the last dosing of study medication

Exclusion criteria

- Clinically diagnosed with Type I diabetes, known diagnosis of maturity onset diabetes of the young (MODY), or secondary diabetes mellitus or known presence of glutamate decarboxylase 65 (GAD65) antibodies
- 2. History of diabetic ketoacidosis, hyperosmolar nonketotic coma, or corticosteroid induced Type 2 diabetes
- 3. Symptoms of poorly controlled diabetes including, but not limited to, marked polyuria, polydipsia, and/or greater than 10% weight loss during the 3 months prior to Enrolment

- 4. FPG >270 mg/dL (>15 mmol/L) assessed based on central laboratory results from Visits 1
- 5. History of diabetes insipidus

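### The baseline HbA1c subgroup model in SAP 4.5.4.3 omits continuous baseline HbA1c and its by-week term, at a small cost in precision

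*SAP*

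**What the plan says.** SAP 4.5.4 defines the primary MMRM with treatment, week and their interaction, plus "continuous fixed covariates of baseline measurement and baseline measurement-by-week interaction".

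SAP 4.5.4.3 opens the subgroup analyses with "The analyses will be based on the primary model (see section 4.5.4") and then fixes two variants:

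- For baseline HbA1c: "The estimates within each baseline HbA1c subgroup will come from the model with terms for treatment, week, baseline HbA1c category, treatment-by-week", and then the two-way and three-way interactions with category. No continuous baseline term appears.
- For the remaining subgroups: the same structure with the subgroup factor in place of the HbA1c category, "as well as the continuous fixed covariates of baseline HbA1c and baseline HbA1c-by-week interaction".

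The interaction test is separate from the estimates: "The model to assess the treatment-by-baseline HbA1c interaction will include baseline HbA1c as a continuous variable", as set out in 4.5.4.2.

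SAP 4.8.5 says "The primary efficacy analysis will be repeated to summarize HbA1c within subgroups", refers to 4.5.4.3 for the model, and adds: "The nominal p-value for the subgroup-by-treatment interaction at week 52 will be presented". The planned outputs are table 27 (change at week 52 by baseline HbA1c) and figure 9 (adjusted mean change over time by baseline HbA1c).

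**The concern.** Baseline HbA1c is the one covariate that the primary model relies on. Replacing it by three categories leaves the variation inside each category unused. Entry requires "Has a HbA1c of ≥7.5% and ≤10.5% based on central laboratory results from Visit 1", so the top category can span 1.5 points (9 to 10.5).

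Because treatment, week and category are fully crossed, the adjusted means with complete data are simply cell means, with nothing adjusted inside a category. All the other subgroup tables would be adjusted for continuous baseline. A category and the continuous value can stand in one model, as the other subgroup models show.

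At stake is the precision of one subgroup display. It could be read more closely if 4.5.4.2 finds a qualitative interaction. The plan would then withhold the comparisons from the original model and summarise the data by baseline category, although 4.5.4.2 does not name a model for that step.

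**Working it through.** **Inputs from the SAP.** SD of change 1.0%, 290 evaluable per arm, margin 0.30%, one-sided 0.025 (section 1.3); entry range 7.5 to 10.5% (Appendix II); categories <8, 8 to <9 and ≥9% (4.5.4.3).

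**The plan's own figure.** n per arm = 2 × (1.960 + 1.645)² × 1.0² / 0.30² = 288.8, so 289 against the stated 290; power at 290 is 95.1%. The sample size reproduces. It does not depend on the subgroup model and only supplies the SD and n used below.

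**Assumptions.** The SAP gives neither the slope b of change on baseline nor the baseline distribution. I take |b| = 0.3 to 0.7, and baseline within 7.5 to 10.5% as uniform, truncated normal (mean 8.3, SD 0.8) or truncated normal (mean 8.2, SD 1.0).

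**Formula.** With s the SD of baseline inside a category, the continuous term explains R² = b²s²/SD² of the variance there. Omitting it enlarges the standard error of the treatment difference by 1/√(1 − R²) − 1.

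| Category | s | b = 0.3 | b = 0.5 | b = 0.7 |
|---|---|---|---|---|
| <8% | 0.143–0.144 | 0.09% | 0.26% | 0.50–0.51% |
| 8 to <9% | 0.281–0.289 | 0.36–0.38% | 1.00–1.06% | 1.99–2.11% |
| ≥9% | 0.334–0.433 | 0.50–0.85% | 1.42–2.43% | 2.84–4.94% |

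The largest entry, with uniform baseline in ≥9%: s = 1.5/√12 = 0.433; R² = 0.7² × 0.433² = 0.092; 1/√0.908 − 1 = 4.9%. At an extreme slope of 1.0 the loss in ≥9% would be about 6 to 11%.

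**In HbA1c points** (b = 0.5, truncated normal 8.3/0.8, about 68, 158 and 65 per arm): the 95% CI half-width, 1.96 × √(2/n) without the covariate and multiplied by √(1 − R²) with it, goes from 0.337 to 0.336, from 0.221 to 0.219 and from 0.344 to 0.339.

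**Chance imbalance.** It shifts an estimate with SD b × s × √(2/n). In ≥9% this is 0.5 × 0.334 × √(2/65) = 0.029 points. It is already part of the category model's standard error: (0.339/1.96)² + 0.029² = 0.0299 + 0.0008 = 0.0308 = 2/65.

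**Simulation** (4000 runs, complete week 52 data, b = 0.5, truncated normal 8.3/0.8): the standard error ratios, category only against category plus continuous baseline, were 1.004, 1.009 and 1.013. Both estimators averaged within 0.002 of the true difference of zero.

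**With values after rescue removed.** A second simulation had four late visits, rescue at HbA1c >8.0% with 50% or 100% uptake, slopes 0.3 to 0.7 and 600 runs per scenario. It gave ratios of 1.00–1.02, 1.00–1.04 and 1.00–1.04. The mean difference between the two models was at most about 0.007 points.

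**Evaluation point.** Under an assumed right-skewed baseline with overall mean 8.30% and mean 9.51% in ≥9%, adjusted means taken at the overall mean would move the ≥9% within-arm mean by 1.21 × 0.3 = 0.36 to 1.21 × 0.7 = 0.85 points. The treatment difference would not move, because the slope is common to the arms.

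**The case against.** The strongest reply is that this is a readable, deliberate specification. The lead-in of 4.5.4.3 is general and the term lists are specific, and 4.8.5 defers to 4.5.4.3. A reader might infer that the SAP contradicts itself; it does not, and a programmer has one instruction to follow. Baseline HbA1c also remains in the model in categorised form, because here it is itself the subgroup variable. All of this stands. The specification is clear but somewhat inefficient.

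A reader might also infer that imbalance inside a category biases the estimates. Under randomisation it is chance, both models are unbiased, and the category model's standard error already contains it. Lost precision and uncorrected imbalance are therefore one effect, not two.

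Nor should a variance figure be read as the loss in interval width. The worst entry above is 1/0.908 − 1 = 10% in variance but 4.9% in standard error. Calling ≥9% the smallest category would also go beyond the SAP, which gives no baseline distribution. Under one assumption above it has about 65 per arm against 68 in <8%.

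Finally, adding the terms has a drawback if the evaluation point is left at the overall mean, since the means in the outer categories would then describe a baseline outside those categories. That stands, and the fix deals with it.

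**Conclusion.** A minor point. The category model leaves out two terms that the primary model and all other subgroup models keep, and the SAP gives no reason. Under the assumed slopes and distributions the standard error is larger by about 0.1–0.5% (<8%), 0.4–2% (8 to <9%) and 0.5–5% (≥9%). These ranges rest on complete week 52 data. Removing values after rescue can raise the loss in the two lower categories somewhat, to at most about 2% and 4% in the simulation. Baseline values from Visit 2 may fall outside 7.5 to 10.5%, which would widen the outer categories and add a little more.

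The primary non-inferiority analysis and the testing hierarchy are unaffected. The interaction test already uses continuous baseline, and its p-value is nominal.

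**What to change.** In 4.5.4.3, add continuous baseline HbA1c and its interaction with week to the baseline HbA1c category model. State that the adjusted means for each category are evaluated at that category's own mean baseline HbA1c, pooled over the three arms, and not at the overall mean. Say that table 27 uses this model, and whether figure 9 does. If the omission is intended, one sentence giving the reason would do instead.

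The change needs no new data and adds two terms to one model. The small cost is that the evaluation point must be specified in the program for each category. It should be made before unblinding.
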